### 7.2.3.1.4. Multiple Imputation

For each missing value of the primary endpoint status, a list of  $m$  ( $m = 5$ ) imputed values will be generated through multiple imputation method and replaced for the missing value. The primary endpoint status is a dichotomous variable with values of responder and nonresponder; thus, logistic regression imputation method will be used to impute missing values of the primary endpoint status. In the logistic regression imputation method, a logistic regression model is fitted for the primary endpoint status variable with a set of covariates constructed from the effects, where the set of covariates is listed in Section 7.2.3.1.3 plus treatment group. The sample SAS code for multiple imputation is included in [Appendix E](#).

After multiple imputation,  $m$  imputed complete datasets will be generated. For each of  $m$  imputed datasets, the proportion of subjects who achieve primary endpoint will be summarized by treatment group. The combined results from  $m$  imputed data on proportion of subjects who achieve the primary endpoint will also be summarized, where the combined proportion is the average of the estimated proportion from each of  $m$  imputed datasets.

For each of  $m$  imputed datasets, a logistic regression model will be fitted for the primary endpoint status variable with treatment group, JAK2V617F mutation status, screening platelet count ( $\geq 1000 \times 10^9/L$  or  $< 1000 \times 10^9/L$ ), and prior anagrelide use (yes vs no) as covariates.

Additional multiple imputation methods may be explored to assist assessing the robustness of the primary endpoint due to missing value.

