## APPENDIX E. SAMPLE SAS CODE

Below is the sample SAS code for multiple imputation of the primary endpoint status.

```
PROC MI DATA=ANAL NIMPUTE=5 SEED=8554633463 OUT=ANAL_MI;  
  CLASS Resp Treat JAK2V617F Plat_BS Infection Trauma Anagre_use;  
  MONOTONE LOGISTIC(Resp = Treat JAK2V617F Plat_BS Infection  
    Trauma PLAT WBC Hemoglobin Anagre_use/ details);  
  VAR Treat JAK2V617F Plat_BS Infection Trauma PLAT WBC Hemoglobin  
    Anagre_use;  
RUN;
```

Below is the sample SAS code to analyze the multiple imputed datasets:

```
PROC LOGISTIC DATA=ANAL_MI;  
  CLASS Resp Treat JAK2V617F plat_screen Anagre_use;  
  MODEL Respo = Treat JAK2V617F plat_screen Anagre_use;  
  By _Imputation_;  
  ODS OUTPUT ParameterEstimates=lgsparms;  
RUN;  
  
PROC MIANALYZE PARMS=LGSPARMS;  
  MODELEFFECTS Treat JAK2V617F plat_screen Anagre_use;  
RUN;
```

| Table No.     | Title  | Population | Standard | In-Text    |
|---------------|--|------------|----------|------------|
| 2.1.13        | Sensitivity Analysis of Proportion of Subjects Achieving the Primary Response – JAKV617F Mutation Change                             | ITT        |          |            |
| 2.1.14        | Sensitivity Analysis of Proportion of Subjects Achieving the Primary Response – Multiple Imputation                                  | ITT        |          |            |
| 2.2           | Summary of Duration of Response  | ITT        |          | X          |
| 2.3.1         | Proportion of Subjects Achieving ELN Response at Week 32   | ITT        |          | X          |
| 2.3.2         | Sensitivity Analysis of Proportion of Subjects Achieving ELN Response at Week 32 – JAKV617F Mutation Change                          | ITT        |          |            |
| 2.3.3         | Proportion of Subjects Achieving ELN Complete Response at Week 32  | ITT        |          |            |
| 2.3.4         | Proportion of Subjects Achieving ELN Partial Response at Week 32   | ITT        |          |            |
| [REDACTED]    | [REDACTED]   | [REDACTED] |          | [REDACTED] |
| [REDACTED]    | [REDACTED]   | [REDACTED] |          | [REDACTED] |
| [REDACTED]    | [REDACTED]   | [REDACTED] |          |            |
| [REDACTED]    | [REDACTED]   | [REDACTED] |          |            |
| [REDACTED]    | [REDACTED]   | [REDACTED] |          |            |
| [REDACTED]    | [REDACTED]   | [REDACTED] |          |            |
| [REDACTED]    | [REDACTED]   | [REDACTED] |          |            |

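### SAP Appendix E cannot impute or analyse the endpoint as printed; once its two name slips are repaired, the pooled treatment coefficient is half the log odds ratio unless coding and event level are stated

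*SAP*

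**What the plan says.** SAP Section 7.2.3.1 triggers a missing-data sensitivity analysis if more than 10% of subjects have missing primary endpoint status. Section 7.2.3.1.4 sets out the method. Status is imputed five times by logistic regression on treatment and the Section 7.2.3.1.3 covariates. Response proportions by arm are reported for each completed dataset and averaged. Then, for each dataset, "a logistic regression model will be fitted for the primary endpoint status variable with treatment group" and the three stratification factors as covariates. The endpoint is described in words only: "The primary endpoint status is a dichotomous variable with values of responder and nonresponder". The section does not say how the five treatment effects are combined, which response level is the event, or how treatment is coded. It refers to Appendix E for sample code.

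Appendix E has three steps:

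- **Imputation.** The target is set by "MONOTONE LOGISTIC(Resp = Treat JAK2V617F Plat_BS Infection". The variable list reads "VAR Treat JAK2V617F Plat_BS Infection Trauma PLAT WBC Hemoglobin" and ends on the next line with `Anagre_use`.
- **Analysis.** The class statement is "CLASS Resp Treat JAK2V617F plat_screen Anagre_use", with no options. The model is "MODEL Respo = Treat JAK2V617F plat_screen Anagre_use", also with no response option.
- **Pooling.** PROC MIANALYZE uses "MODELEFFECTS Treat JAK2V617F plat_screen Anagre_use", with no rescaling or exponentiation.

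**The concern.** Two faults are visible on the page: the variable to be imputed is not in the imputation variable list, and the analysed variable is not the imputed one. A programmer will notice both and repair them.

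The next fault would not stop a run. With the names repaired, the code yields a Treat estimate whose scale and sign depend on defaults that the SAP does not mention. The primary analysis (SAP Section 7.2.1) reports a stratum-adjusted odds ratio with a 95% confidence interval, which is the natural comparator for a pooled treatment effect. If the pooled coefficient were exponentiated and set beside it, imputation would seem to have shrunk, or even reversed, the treatment effect when only the parameterisation had changed.

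The trigger is within easy reach. Section 7.2.3.1.1 makes status missing for every subject who stops treatment before Week 32. Ten percent of 120 is 12, so 13 subjects suffice.

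**Working it through.** The plan states no figure for this point, so there is none to reproduce.

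**Step 1. Names, side by side (Appendix E).**

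| Statement | Endpoint variable |
|---|---|
| PROC MI CLASS | `Resp` |
| PROC MI MONOTONE LOGISTIC target | `Resp` |
| PROC MI VAR | absent |
| PROC LOGISTIC CLASS | `Resp` |
| PROC LOGISTIC MODEL | `Respo` |

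The code is legible and the VAR statement closes normally, so this is not a redaction or extraction gap. As printed, the endpoint is outside the imputation set and the model has no valid response. Nothing reaches the pooling step.

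**Step 2. Scale, once the names are repaired.** Assumption from software knowledge: without options, PROC LOGISTIC codes a two-level CLASS variable +1/−1. Write a for the intercept and b for the Treat coefficient:

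- logit(p, ruxolitinib) = a + b
- logit(p, anagrelide) = a − b
- the difference is the log odds ratio = 2b, so b = log OR / 2

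Inputs: 30% vs 5% from SAP Section 3.3, used only to size the effect.

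- OR = (0.30/0.70) / (0.05/0.95) = 8.14
- log OR = 2.097
- b = 2.097/2 = 1.049 in magnitude
- exp(1.049) = 2.85; exp(−1.049) = 0.35

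The standard error halves too, so the confidence limits are also half-scale and the test statistic is unchanged.

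**Step 3. Check by simulation.** I simulated one trial of 120 subjects (18/60 vs 3/60 responders), made 23 statuses missing, and used m = 5 with Rubin's rules. This illustrates the algebra and does not forecast the trial. The models were fitted outside SAS with each coding set explicitly; no SAS run was made.

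| Coding | Pooled coefficient (SE) | exp | t | p |
|---|---|---|---|---|
| Reference (0/1) | 2.646 (0.764) | 14.1 | 3.462 | 0.00057 |
| Effect (+1/−1) | 1.323 (0.382) | 3.75 | 3.462 | 0.00057 |

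The square root of 14.1 is 3.75, as the algebra requires.

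**Step 4. Sign.** Again from software knowledge, the default models the first-ordered response level. The label Nonresponder sorts before Responder, and 0 before 1, so either coding would model nonresponse. A coding of 1 for responder and 2 for nonresponder would model response. The sign also depends on which Treat level is displayed. Effect-coded results from the same simulation:

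| Event modelled | Treat level displayed | Coefficient |
|---|---|---|
| Response | Ruxolitinib | +1.323 |
| Response | Anagrelide | −1.323 |
| Nonresponse | Ruxolitinib | −1.323 |
| Nonresponse | Anagrelide | +1.323 |

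The documents do not give the stored coding of either variable.

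**The case against.** The best defence is that this is labelled sample code. The prose in Section 7.2.3.1.4 describes a sound imputation model, and the two naming slips would stop the run and be caught. The SAP never says that the pooled coefficient will be exponentiated. The planned table for this analysis (2.1.14) is titled as a comparison of proportions, and those proportions do not use the coefficient. They would also appear alongside it, so an odds ratio of 2.85 or 0.35 next to roughly 30% vs 5% should look wrong to a careful reader.

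Most of this stands as a limit on the size of the problem, and four stronger readings fail because of it:

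- A reader might infer that the printed code pools a wrong effect. It cannot, because it fails first.
- A reader might infer that the wrong response level is modelled. That depends on stored codings the documents do not give, and nonresponse with anagrelide displayed gives the right sign.
- A reader might infer that nothing would reveal the error. The by-arm proportions could.
- A reader might infer that this is the SAP's only treatment of missing data. Section 7.2.3.1.2 adds by-arm displays, Section 7.2.3.1.4 allows further imputation methods, and the primary analysis counts missing visits as not controlled.

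The defence does not answer the gap in the prose. Because Section 7.2.3.1.4 is silent on combining treatment effects, Appendix E is the only specification of that step. Repairing the names does not prompt anyone to add the coding options.

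**Conclusion.** Appendix E is wrong as printed, and two lines show it without any assumption about defaults: `Resp` is missing from the VAR list, and `Respo` does not exist. After those repairs, the pooled Treat coefficient and its limits are half the log odds ratio, provided PROC LOGISTIC applies its default effect coding. Read as an odds ratio at the planning rates, the result would be 2.85 (or 0.35) instead of 8.14. The event level and the direction of the treatment contrast are unspecified. They are not shown to be wrong.

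The consequence is confined to the pooled effect estimate and interval of one conditional sensitivity analysis, and arises only if they are read as the treatment log odds ratio. Coding does not change the p-value or the imputed proportions, although the proportions do need the imputation step to run. A reader might infer a threat to the primary result; there is none, because the CMH analysis does not use this code. The correction should be made because it is cheap and not a matter of judgement.

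**What to change.** In SAP Appendix E:

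1. Add `Resp` as the last variable in the PROC MI VAR list.
2. Change `Respo` to `Resp` in the PROC LOGISTIC model.
3. Add `PARAM=REF` to the PROC LOGISTIC CLASS statement, name anagrelide as the reference arm, and use `EVENT=` on the response to name responder as the event. Use the values actually stored in the analysis dataset.

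In SAP Section 7.2.3.1.4, add one sentence: the treatment log odds ratios are combined by Rubin's rules, and the pooled estimate and 95% confidence limits are exponentiated and reported beside the CMH odds ratio.

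The cost is a few lines of code and one sentence, with no change to data collection, sample size or the primary analysis. A test run of all three steps on dummy data, checking the pooled odds ratio against the by-arm proportions, would confirm the repair.

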### Figures

| Figure No. | Title  |
|------------|--|
| 4.2.1      | Plot of Odds Ratios by Subgroups   |
| 4.2.2      | Kaplan-Meier Estimates of Duration of Response (ITT)                             |
| 4.2.3      | Kaplan-Meier Estimates of Time to Treatment Discontinuation (ITT)                |
| ████       | ██ |
| ████       | ██ |
| 4.2.6      | Line Graph of Mean Change From Baseline for Selected Laboratory Values (Safety)  |

### Listings

| Listing No. | Title  |
|-------------|--|
| 2.1.1       | Analysis Population  |
| 2.1.2       | Subject Enrollment and Disposition Status  |
| 2.1.3       | Subject Inclusion and Exclusion Criteria   |
| 2.2         | Protocol Deviations  |
| 2.4.1       | Demographic and Baseline Characteristics   |
| 2.4.2       | Disease History  |
| 2.4.3       | Medical History  |
| 2.4.4       | Prior and Concomitant Drug Treatments  |
| 2.6.1       | Primary Response   |
| 2.6.2       | Duration of Primary Response   |
| 2.6.3       | ELN Response Status  |
| ████        | ██ |
| ████        | ██ |
| ████        | ██ |
| 2.6.7       | Bone Marrow Biopsy   |
| 2.6.8       | ECOG Status  |
| 2.7.1       | Study Drug Administration and Compliance   |

| Listing No. | Title  |
|--------------------|---|
| 2.7.2              | Adverse Events  |
| 2.7.3              | Treatment-Related Adverse Events                        |
| 2.7.4              | Serious Adverse Events                                  |
| 2.7.5              | Adverse Events Leading to Death                         |
| 2.7.6              | Adverse Events Leading to Discontinuation of Study Drug |
| 2.7.7              | Adverse Events Leading to Withdrawal From Study         |
| 2.8.1              | Clinical Laboratory Values - Hematology                 |
| 2.8.2              | Clinical Laboratory Values - Chemistry                  |
| 2.8.3              | Abnormal Clinical Laboratory Values - Hematology        |
| 2.8.4              | Abnormal Clinical Laboratory Values - Chemistry         |
| ████               | ████████████████████                                    |
| 2.8.6              | Bone Marrow Biopsy                                      |
| 2.9.1              | Vital Signs   |
| 2.9.2              | Abnormal Vital Sign Values                              |
| 2.9.3              | Alert Vital Sign Values                                 |
| 2.10.1             | Clinically Notable ECG Abnormalities                    |
| 2.11.1             | Physical Examinations                                   |
